#### Treatment Period (16 weeks)

The 16-week Treatment Period includes a 3-week Titration Period followed by a 1-week Stabilization Period and a 12-week Maintenance Period. Four weeks after the Screening Visit (Visit 1), subjects will return to the clinic for the Baseline Visit (Visit 2, Day 1). Subjects who continue to fulfill the inclusion and exclusion criteria will be randomized to 1 of the 4 treatment arms in a 1:1:1:1 ratio (using random permuted blocks to ensure balanced randomization across the 4 treatment arms). Randomization will be stratified by current use of AEDs that bind to

SV2A proteins (LEV or brivaracetam) and by region (Europe, North America, Japan, and China) at the time of randomization.

During the entire 16-week Treatment Period, the dose of concomitant AEDs and the settings for neurostimulation devices must remain stable.

After the Baseline Visit (Visit 2), regular visits will be scheduled for the remainder of the Treatment Period.

#### *Titration Period (3 weeks)*

Investigational medicinal product will be increased approximately every 3 to 7 days depending on treatment arms (refer to [Table 7-1](#) for details). Subjects will be instructed to take the IMP in 2 equally divided doses, approximately 12 hours apart in the morning and evening.

Subjects who cannot tolerate IMP through Week 3 will be withdrawn from the study.

#### *Stabilization Period and fallback (1 week)*

Subjects who tolerate IMP will continue with their target dose throughout the Stabilization Period. For subjects with tolerability issues at their target dose, one fallback to a predefined dose based on the randomized dose ([Table 7-2](#)) will be allowed during the Stabilization Period and should occur at least 2 days prior to the start of the Maintenance Period (Visit 4) for subjects who experience tolerability issues during Week 4. The Study Physician or delegate should be consulted prior to use of the fallback option and the date as well as the reason for fallback will be recorded in the source documents and in the electronic Case Report form (eCRF).

Fallback may be managed via an unscheduled visit. Fallback IMP packs will be allocated via the interactive response technology (IRT). After fallback, the dose will be kept stable for the rest of the Maintenance Period. Further dose changes (ie, titration) are not allowed. Subjects who are not able to tolerate the IMP during titration and after the fallback will be tapered off IMP in a blinded fashion and will be withdrawn from the study.

#### *Maintenance Period (12 weeks)*

At Visit 4 (at the end of the Stabilization Period), subjects will enter a 12-week Maintenance Period during which they will receive their target dose (or their fallback dose, if applicable). During the entire 12-week Maintenance Period, the dose of IMP (target dose or fallback dose) and concomitant AEDs must remain stable. Subjects must return to the clinic for scheduled visits as outlined in [Table 5-1](#).

Subjects who complete the Maintenance Period or who discontinue early from the study will return for an End of Treatment Visit or Early Discontinuation Visit (EDV), respectively.

Subjects completing the Maintenance Period will have the opportunity to enroll into the OLE study, EP0093. They will be converted to the entry dose of the EP0093 study, 200mg bid.

Subjects withdrawing from the study or deciding not to participate in the OLE study (EP0093) will be tapered off the IMP.

*For subjects discontinuing the study early or not enrolling in the OLE study:*

#### Taper Period (4 weeks)

The 4-week Taper Period will be required for subjects who choose not to enroll in the OLE study or who discontinue the study. Subjects entering the 4-week Taper Period should be gradually

tapered off the IMP over a 3-week period (Table 7-3) followed by a 1-week drug-free period. A faster or slower taper schedule than the suggested 3 weeks may be implemented, if medically necessary, as per the Investigator's medical judgment. Subjects will start their taper at the EDV/End of Treatment Visit (Visit 7) and will return 1 week after last intake of IMP for the End of Taper Visit (Visit 8). Changes to concomitant AED(s) are not allowed during the taper of PSL unless they are medically necessary as per the Investigator's medical judgment to treat rebound seizures.

#### Safety Follow-up Period (1 month)

Safety follow up for all subjects not entering the OLE will consist of 1 required visit, 30 days after the last IMP intake (Week 23 or sooner in case of early discontinuation), including an echocardiogram. An additional follow-up echocardiogram will be performed at 6 months ( $\pm 1$  month) after the last IMP intake only for subjects exposed to IMP for more than 3 weeks.

*For subjects continuing to the OLE study:*

#### Conversion Period (3 weeks)

The 3-week Conversion Period will be required for subjects who choose to enroll in the OLE study at the end of the Maintenance Period. Doses for those participating in the 3-week Conversion Period will be gradually adapted (increased or decreased) in a blinded way to reach the entry dose for the OLE. Subjects who take placebo during the Maintenance Period will receive PSL titrated to the target dose.

### **5.1.1 Study duration per subject**

The total duration of the study per subject will be up to 27 weeks with a maximum of 19 weeks exposure to PSL. An additional follow-up echocardiogram will be performed at 6 months ( $\pm 1$  month) after the last IMP intake only for subjects exposed to IMP for more than 3 weeks and either discontinuing the study or not entering the OLE.

The end of the study is defined as the date of the last SFU Visit (30 days after the last IMP intake) of the last subject in the study. Additionally, the reporting of SAEs will continue until the 6-month follow-up echocardiogram.

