### 11.1.2.3 Additional procedures for reporting serious adverse events

If an SAE is reported, UCB must be informed within 24 hours of receipt of this information by the site (see contact information for SAE reporting listed in the SAE Reporting section at the front of the protocol). The Investigator must forward to UCB (or its representative) a duly completed "Investigator SAE Report Form for Development Drug" (SAE Report form) provided by UCB, even if the data are incomplete, or if it is obvious that more data will be needed in order to draw any conclusions. Information recorded on this form will be entered into the global safety database.

An SAE Report form will be provided to the Investigator. The SAE Report form must be completed in English.

It is important for the Investigator, when completing the SAE Report form, to include the assessment as to a causal relationship between the SAE and the IMP administration. This insight from the Investigator is very important for UCB to consider in assessing the safety of the IMP and in determining whether the SAE requires reporting to the regulatory authorities in an expedited manner. Expedited reporting to regulatory authorities will be in line with local laws.

Additional information (eg, autopsy or laboratory reports) received by the Investigator must be provided to UCB within 24 hours. All documents in the local language must be accompanied by a translation in English, or the relevant information included in the same document must be summarized in the SAE Report form.

The Investigator is specifically requested to collect and report to UCB (or its representative) any SAEs (even if the Investigator is certain that they are in no way associated with the IMP), up to 6 months from the last IMP intake for each subject (ie, until the 6-month follow-up echocardiogram), and to also inform subjects of the need to inform the Investigator of any SAE within this period. Serious AEs that the Investigator thinks may be associated with the IMP must be reported to UCB regardless of the time between the event and the end of the study.

Upon receipt of the SAE Report form, UCB will perform an assessment of expectedness of the reported SAE. The assessment of the expectedness of the SAE is based on the IB.

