2.5.2 Study duration per subject

The total duration of study per subject will be up to 27 weeks with a maximum of 19 weeks exposure to PSL. An additional follow-up echocardiogram will be performed at 6 months (± 1 month) after the last IMP intake only for subjects exposed to IMP for more than 3 weeks and either discontinuing the study or not entering the OLE.

The end of the study is defined as the date of the last SFU Visit (30-days after the last IMP intake) of the last subject in the study. Additionally, the reporting of SAEs will continue until the 6-month follow-up echocardiogram.

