4.3.1 Sequential Analyses for European/North American/Japanese regulatory submissions

Due to COVID-19 pandemic, subjects from the China region (100 in total) were not enrolled, hence this region will not be included in the sequential analyses - gatekeeping procedure mentioned in the protocol.

Once all subjects have completed or terminated the study, data will be locked and unblinded and no changes to these data are allowed after unblinding. Analysis for European/North American/Japanese regulatory submissions will be carried out at 0.05 alpha level (two-sided).

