10.4.3 Echocardiograms

Echocardiogram data are collected at Visit 1, Visit 6, and Visit 9. Depending on the availability of data, echocardiogram abnormalities (Left Ventricle, Left Atrium, Right Ventricle, Right Atrium, Pericardium, Pulmonary Artery Systolic Pressure and overall assessment) will be summarized by treatment group and PSL total group and scheduled visit as the number and percentage of subjects with an abnormality. In addition, Echocardiogram Valvular abnormality grade (Aortic Valve, Mitral Valve, Tricuspid Valve, Pulmonary Valve) described in Appendix 13.4 will be summarized descriptively. Valvular abnormality grade equal or larger than grade 2 is corresponding to valvular abnormal. Subject numbers with abnormality for any assessment will be provided.

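### The end-of-study definition and the SAP safety sections do not cover the protocol's own 6-month echocardiogram and 6-month SAE window

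*Protocol*

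**What the plan says.** Protocol 5.1.1 closes the study at the last 30-day visit: "The end of the study is defined as the date of the last SFU Visit (30 days after the last IMP intake". It then adds: "Additionally, the reporting of SAEs will continue until the 6-month follow-up echocardiogram". Protocol 5.1, under the Safety Follow-up Period, says "An additional follow-up echocardiogram will be performed at 6 months". SAP 2.5.2 repeats the requirement, "at 6 months (± 1 month) after the last IMP intake only for subjects exposed to IMP for more than 3 weeks", and confines it to subjects who discontinue or do not enter the OLE. Protocol 11.1.2.3 asks investigators to report SAEs "up to 6 months from the last IMP intake for each subject (ie, until the 6-month follow-up echocardiogram".

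On analysis, Protocol 13.4.1 plans to list and summarise echocardiograms from baseline, during treatment and after treatment, with changes from baseline. Protocol 4.2.2 and SAP 2.3.2 define the safety variable as valvular, pericardial or other significant abnormality at every centrally read assessment. SAP 10.4.3 says "Echocardiogram data are collected at Visit 1, Visit 6, and Visit 9" and summarises by scheduled visit. SAP 10.2 ends AE recording with the SFU period, 30 days after the last dose. It tabulates serious TEAEs by period for the Treatment Period and its two parts only.

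On timing, Protocol 8.4 records study termination at Visit 9 for subjects who do not enter the OLE. SAP 4.3.1 locks once every subject has completed or terminated: "data will be locked and unblinded and no changes to these data are allowed after unblinding".

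**The concern.** Protocol 2.4 gives cardiac valvular and epicardial lesions in dogs as the reason for echocardiographic monitoring during and after treatment. The 6-month scan is the only routinely scheduled one later than about 30 days off drug. Under footnote k of Protocol Table 5-1, a subject scanned at Visit 6 is excused the 30-day scan. If that subject then does not enter the OLE, the 6-month scan is the only one routinely scheduled off drug.

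Subjects are therefore recalled for a test that has no named place in the summaries. The SAE window has the same gap: the protocol collects for 6 months, and the SAP describes 30 days. SAP 3.9, which lists changes from the protocol, mentions neither point, so this looks like an omission and not a decision. At stake is whether the study report can describe late valve findings and late SAEs in a pre-specified way.

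**Working it through.** **1. Reproduce the stated duration (Protocol 5.1.1: up to 27 weeks, 19 weeks' exposure).**
- Exposure = 16 weeks of treatment + 3 weeks of taper or conversion = 19 weeks.
- Duration = 4 + 16 + 3 + 30/7 = 27.3 weeks. From the schedule, Day -28 to Day 161 is 189/7 = 27.0 weeks.

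Both figures reproduce. The 27 weeks therefore stop at the 30-day SFU Visit.

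**2. Gap from the SFU Visit to the 6-month scan.** Inputs are the scan at 6 ±1 months and the SFU at 30 ±7 days after the last dose, with 1 month = 365.25/12 = 30.44 days. Gap = scan day − 30.

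| Scan | Days after last dose | Gap in days | Gap in months | Weeks from Visit 1 |
|---|---|---|---|---|
| 5 months | 152.2 | 122.2 | 4.0 | 23 + 21.7 = 44.7 |
| 6 months | 182.6 | 152.6 | 5.0 | 23 + 26.1 = 49.1 |
| 7 months | 213.1 | 183.1 | 6.0 | 23 + 30.4 = 53.4 |

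Using the SFU window, the extremes are (152.2 − 37)/30.44 = 3.8 months and (213.1 − 23)/30.44 = 6.2 months. Follow-up for these subjects lasts about 49 weeks (44.7 to 53.4), not 27.

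**3. Share of the SAE window after the SFU.** 152.6/182.6 = 0.84, or about 5 of the 6 months.

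**4. Whose results can fall after lock.** A 6-month result is in hand at lock only if the last dose was about 5 to 7 months earlier. If lock came right after the last SFU Visit (an assumption), subjects whose last dose fell within about 4 to 6 months of the last subject's would be cut off. A lock 4 to 6 months later would cut off almost none. The documents give no lock date, accrual dates or OLE uptake, so no count follows.

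**5. The provisions side by side.**
- Echocardiogram: the protocol plans after-treatment summaries, and the variable covers every assessment. The SAP names Visits 1, 6 and 9. SAP 3.1 keeps unscheduled data out of by-visit summaries. A 6-month result held before lock therefore still has no named time point.
- SAEs: Protocol 11.1.2.3 runs to 6 months and SAP 10.2 to 30 days. Protocol 11.1.3 sends SAEs obtained after lock to the Patient Safety database. Neither document plans to bring them back into the study results.

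**The case against.** A reader might infer that lock is fixed at the 30-day visit and that the 6-month data are never analysed. The documents do not say so. SAP 4.3.1 and Protocol 13.5 tie lock to subjects' completion and to data review. A lock near the last SFU Visit is only a reasonable inference from the Visit 9 termination entry. The bar on changes protects the locked data and does not forbid a later safety cut. Protocol 13.4.1 promises after-treatment summaries, and SAP 1 follows the protocol unless it says otherwise. SAP 3.1 generally lists all CRF data, and post-lock SAEs are retained without time limit.

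A reader might also infer that nearly every 6-month scan is lost because the trial stopped early. That would need dates and OLE uptake that are not given.

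Three further points have force:
- The 6-month scan hangs on the Visit 9 cell of the schedule as a footnote, so the SAP's Visit 9 might be meant to include it.
- The 30-day scan is also off drug, so the 6-month scan is not generally the only look after stopping. Individual safety is further covered by central reading and the DMC.
- The SAP's 30-day AE limit matches the general AE rule in Protocol 11.1.1.1, and its Taper and Safety Follow-up period runs to the date of final contact. The conflict concerns SAEs. The limits on the serious-TEAE tables do not come from the end-of-study definition, and moving that definition would not change them.

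These arguments narrow the point without removing it. If Visit 9 includes the 6-month scan, one label covers results about 5 months apart. A listing is not the summary that the protocol promises.

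**Conclusion.** The concern holds in limited form. The end-of-study definition and SAP 10.2 and 10.4.3 leave out a 6-month echocardiogram and an SAE window that the protocol requires, and SAP 3.9 records no such change. The scan falls about 4 to 6 months after the SFU Visit (3.8 to 6.2 with its window), and about five sixths of the SAE window lies beyond day 30.

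The missing echocardiogram time point does not depend on when lock occurs. The risk of results arriving after lock does. It rests on lock following soon after the last SFU Visit, and for the echocardiogram it concerns only later finishers with more than 3 weeks of IMP who do not enter the OLE. Their number is unknown. The documents do not support saying that the data are never analysed or that most of them are lost.

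**What to change.** - Add a 6-month follow-up time point to SAP 10.4.3, separate from Visit 9: valve grade, pericardium and change from baseline, for all subjects with a result.
- Reconcile the AE window in SAP 10.2 with the 6-month SAE window in Protocol 11.1.2.3, and add a listing or table of SAEs after the SFU Visit.
- Keep the current lock, and pre-plan a later safety data cut and CSR addendum for echocardiograms and SAEs that arrive after it.

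The cost is some SAP wording and one small extra safety output, on data that the protocol already collects. The end-of-study definition does not need to move. Moving it to the last 6-month scan would take a protocol amendment and could delay lock and the primary analysis by months.

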### **5.1.2 Planned number of subjects and sites**

The enrollment goals are 500 subjects in the Europe/North America/Japan regions and approximately 125 subjects in China at approximately 300 sites worldwide. Assuming a 20% screen failure rate, approximately 400 and approximately 100 subjects will be randomized in the Europe/North America/Japan regions, and China, respectively. Because the time from protocol submission to first patient first visit (FPFV) may be longer in China, subjects enrolled in China will be in addition to the 400 subjects randomized in Europe/North America/Japan, in order to support the possibility of conducting 2 sequential analyses to maintain the blind as described in Section 13.2 and Section 13.3.1.

### **5.1.3 Anticipated regions and countries**

The study will be conducted in Europe, North America, Japan, and China, with possible extension to other regions or countries.

---

## 5.2 Schedule of study assessments

The schedule of assessments is presented in [Table 5-1](#).

This document cannot be used to support any marketing authorization application and any extensions or variations thereof.

REDACTED COPY

**Table 5-1: Schedule of assessments**

Visit	BL Period (4 weeks)	Treatment Period (16 weeks)										SFU Period (30 days after IMP intake)	Unsch Visit b	
		Titration Period (3 weeks)			Stab Period (1 week)	Maintenance Period (12 weeks)				Taper/Conversion Period (3 to 4 weeks) a				
		V2 BL	TC	V3	TC	V4	V5	V6	V7 (EDV/EOT)	TC	V8 (Conversion)			V8 (Taper)
Wk -4	D 1	Wk 1	Wk 2	Wk 3	Wk 4	Wk 8	Wk 12	Wk 16		Wk 19	Wk 20	Wk 23		
Day Number	-28	1	7	14	21	28	56	84	112		133	140	161	
Visit Window (days)		±3	±3	±3	±3	±7	±7	±7	±7		±7		±7	
Assessments														
Written informed consent	X													
Call IRT to obtain subject number and dispensation of Subject Trial Card	X													
Demographic data	X													
Habits and lifestyle	X													
Verification of inclusion/exclusion criteria	X	X												
Verification of withdrawal criteria		X	X	X		X	X	X	X					
General medical/procedures history	X													
Epilepsy history including etiology, diagnosis, surgery, and seizure history	X													
Documentation of MRI (within 10 years)	X													

**Table 5-1: Schedule of assessments**

Visit	BL Period (4 weeks)	Treatment Period (16 weeks)										Taper/Conversion Period (3 to 4 weeks) a	SFU Period (30 days after IMP intake)	Unsch Visit b
		Titration Period (3 weeks)			Stab Period (1 week)	Maintenance Period (12 weeks)								
		V2 BL	TC	V3	TC	V4	V5	V6	V7 (EDV/EOT)	TC	V8 (Conversion)			
Week Number	Wk -4	D 1	Wk 1	Wk 2	Wk 3	Wk 4	Wk 8	Wk 12	Wk 16		Wk 19	Wk 20	Wk 23	
Documentation of video-EEG c	X													
AED history	X													
Randomization (IRT)		X												
C-SSRS Baseline d	X													
C-SSRS since last visit d,e		X		X		X	X	X	X		X		X	
HADS d		X				X			X				X	
SSG d		X				X			X				X	
QOLIE-31-P d		X				X			X				X	
CIWA-B d									X		X		X	
TSQM-9 d									X					
Vital signs f	X	X		X		X	X	X	X		X		X	
Body weight and height g	X	X				X	X	X	X		X		X	
Physical examination h (XF=Full; XB=Brief)	XF	XB				XB			XF		XF		XB	
Neurological examination i (XF=Full; XB=Brief)	XF	XB				XB			XF		XF		XB	

**Table 5-1: Schedule of assessments**

Visit	BL Period (4 weeks)	Treatment Period (16 weeks)										SFU Period (30 days after IMP intake)	Unsch Visit b	
		Titration Period (3 weeks)			Stab Period (1 week)	Maintenance Period (12 weeks)				Taper/Conversion Period (3 to 4 weeks) a				
		V2 BL	TC	V3	TC	V4	V5	V6	V7 (EDV/EOT)	TC	V8 (Conversion)			V8 (Taper)
Wk -4	D 1	Wk 1	Wk 2	Wk 3	Wk 4	Wk 8	Wk 12	Wk 16		Wk 19	Wk 20	Wk 23		
Psychiatric and Mental Status		X		X		X	X	X	X		X		X	
12-lead ECG j	X	X		X		X	X		X		X		X	
Echocardiogram k	X							X					X l	
Blood/urine sample for clinical laboratory analyses	X	X				X		X	X		X		X	
Blood sample for concomitant AED assay m,n	X	X						X	X					
Blood sample for PSL PK analysis o,n				X		X	X	X	X					
Pregnancy test p	X	X		X		X	X	X	X		X		X	
Diary dispensing (provide instructions on proper completion)	X	X		X		X	X	X	X		X		X	
Seizure evaluation (count & type) q		X	X	X	X	X	X	X	X	X	X		X	
Concomitant medications (AEDs and non-AEDs) and procedures	X	X	X	X	X	X	X	X	X	X	X		X	
Recording of adverse events	X	X	X	X	X	X	X	X	X	X	X		X	

**Table 5-1: Schedule of assessments**

Visit	BL Period (4 weeks)	Treatment Period (16 weeks)										Taper/Conversion Period (3 to 4 weeks) a	SFU Period (30 days after IMP intake)	Unsch Visit b	
		Titration Period (3 weeks)			Stab Period (1 week)	Maintenance Period (12 weeks)									
		V2 BL	TC	V3	TC	V4	V5	V6	V7 (EDV/EOT)	TC	V8 (Conversion)				V8 (Taper)
Week Number	Wk -4	D 1	Wk 1	Wk 2	Wk 3	Wk 4	Wk 8	Wk 12	Wk 16		Wk 19	Wk 20	Wk 23		
Health-related outcomes and HRU	X	X		X		X	X	X	X			X		X	
IMP dispensing (IRT)		X		X		X	X	X	X						
IMP accountability and return f				X		X	X	X	X			X			
Study termination g												X		X	

AED=antiepileptic drug; BL=Baseline; CIWA-B=Clinical Institute Withdrawal Assessment-Benzodiazepines; C-SSRS=Columbia-Suicide Severity Rating Scale; D=day; DBP=diastolic blood pressure; ECG=electrocardiogram; EDV=Early discontinuation Visit; EEG=electroencephalogram; EOT=End of Treatment; HADS=Hospital Anxiety and Depression Scale; HRU=healthcare resource utilization; IMP=investigational medicinal product; IRT=interactive response technology; MRI=magnetic resonance imaging; OLE=open-label extension; PK=pharmacokinetic; PSL=padsevonil; QOLIE-31-P=Quality of Life Inventory in Epilepsy-31-P; SBP=systolic blood pressure; SFU=Safety Follow-Up; SSG=Seizure Severity Global Item; Stab=Stabilization Period; TC=telephone call; TSQM=Treatment Satisfaction Questionnaire for Medication; Unsch=unscheduled; V=visit; Wk=Week

a Taper Period, for subjects who choose not to enter OLE study EP0093, will last for 3 weeks plus 1 week of drug-free period. Conversion Period, for subjects who choose to enter OLE study EP0093, will last for 3 weeks.

b At any time, the subject may have an additional study visit if the Investigator or the subject and/or legal representative deem it necessary. Appropriate assessments will be conducted in relation to the reason for the visit.

c Epileptic seizures must have been documented using video-EEG recording in the past (description or report must be available). The Investigator must consult with the UCB Study Physician or representative for confirmation of eligibility as per instructions in the Study Manual.

d Questionnaires to be completed by all subjects prior to any other study procedures at the visit. The CIWA-B will only be completed by subjects tapering.

e If an unscheduled visit is conducted due to safety or efficacy reasons, a C-SSRS assessment will be performed with the subject during the visit. If an unscheduled visit is conducted for reasons other than safety or efficacy concerns (eg, replacement of lost medication, repeated collection of a laboratory specimen due to collection, or analysis issues), a C-SSRS will not be required at these visits.

f Vital signs measured in supine position after 5 minutes of rest include pulse rate, respiratory rate, SBP, and DBP.

[figure not shown]
[figure not shown]
g Height will only be measured at Visit 1.

- h Full physical examinations will assess cardiac and respiratory function via auscultation and review of the following body systems: general appearance; ear, nose, and throat; eyes; hair and skin; respiratory; cardiovascular; gastrointestinal; musculoskeletal; hepatic; neurological; and mental status. Brief physical examinations will include a review of the following body systems: general appearance (including mental status); skin; respiratory; cardiovascular; gastrointestinal; and hepatic.
- i Brief neurological examination will include a general assessment and evaluation of reflexes, muscle strength and coordination, and cerebellar function. Full neurological examinations will include in addition, evaluation of cranial nerves, motor system (general muscle strength and tone), and sensations in upper/lower extremities.
- j Baseline ECG has to be scheduled and results received before Visit 2. An ECG at the SFU Visit will be performed only if abnormal at the End of Treatment or Early Discontinuation Visit. All ECG recordings will be performed with the subject resting in the supine position for at least 5 minutes.
- k The echocardiogram will be conducted at Visit 1. Echocardiograms will be repeated at Visit 6 for subjects continuing into the OLE study. Subjects discontinuing will have an echocardiogram 30 days after last IMP intake at the SFU Visit (except if performed at Visit 6). A repeat echocardiogram will be performed for subjects with a new finding, Grade 2 (moderate severity), or Grade 3 (severe severity).
- l An echocardiogram will also be performed 6 months after last IMP intake for subjects exposed to >3 weeks to IMP and discontinuing the study (but not for subjects with <3 weeks exposure).
- m AED samples will ideally be taken immediately prior to dose of concomitant medication on each occasion. If this is not possible, then the sample may be taken at any time after dose and the timing of sample in relation to dose should be kept the same ( $\pm 1$  hour) on each occasion for each subject. Therefore, the timing of visits for each subject when AED samples are collected should be scheduled approximately at the same time whenever possible. Assay of parent PSL and metabolites may be included in the AED panel of tests at Visits 6 and 7.
- n On Visits 6 and 7, unless the concomitant AED sample is within  $\pm 5$  minutes of a scheduled MITRA® sample for PSL assay, a separate, additional MITRA sample will be taken at same time as the concomitant AED blood sample.
- o Subjects are requested to provide blood samples for measurement of PSL PK whenever possible. On Visits 3, 5, and 6, site personnel should obtain blood samples, via MITRA microsampling, for measurement of random PSL levels at any time between IMP intakes and record accurately the time of last IMP intake and the time of sample collection. On Visits 4 and 7, blood samples, via MITRA microsampling, for measurement of sparse PK profiles will be collected as follows: immediately before IMP intake (maximum 15 minute before intake) and then 3 times after (between 30 minutes and 3 hours after IMP intake), taken at least 30 minutes apart. All samples may be taken either at home or in the site or partly at home and partly at the site.
- p For all female subjects, serum pregnancy test at Visits 1 and 7 (in case the subject enters into the OLE study) and where applicable. Urine pregnancy test will be used at other visits for female subjects of childbearing potential.
- q Seizure counts are collected on the subject's daily record card on a daily basis.
- r At each visit following an IMP dispensation, IMP should be presented to check for compliance.
- s Study termination will occur at Visit 8 only for subjects enrolling in OLE study, EP0093. The SFU Visit will be performed only for subjects who do not enter the OLE study, EP0093.

